My long-term goal is to promote successful aging among persons with chronic HIV-1 infection by strategies to optimize physical function and minimize disability and frailty. The primary objective of this proposal is to investigate the GH/IGF-I axis as a potential pathway of early functional impairment in persons aging with HIV. My research is anticipated to advance understanding of the mechanisms and interactions of the GH/IGF-I axis in physical function. My central hypothesis is that a phenotype of accelerated functional impairment observed among some persons with HIV infection will be associated with disruption in the GH/IGF-I axis (the somatopause). This hypothesis will be evaluated through the following specific aim:

**Specific Aim 1: Determine the impact of high or moderate intensity combined resistance (REx) and cardiovascular exercise (CEx) on physical function in older HIV+ (n=36) and HIV- (n=36) adults.**

Approach: Previously sedentary older adults (aged 50-75 years) will undergo a 24 week REx + CEx exercise training intervention.

Hypothesis 1a: Both HIV+ and HIV- older adults will have a significant improvement in physical function (chair rise time) with REx + CEx, but HIV+ will have a *lower* increase than HIV- older adults.

Hypothesis 1b: Both HIV+ and HIV- older adults randomized to a high intensity REx + CEx intervention will have greater improvement in physical function than those randomized to the moderate intensity exercise.

Hypothesis 1c: Utilizing established techniques for screening and training, moderate intensity exercise followed by randomization to either continue a moderate- or progress to high- intensity exercise will result in minimal or no adverse events and will result in similar completion rates, with 80% of participants completing the training program.

**Specific Aim 2: Determine the impact of high or moderate intensity combined REx and CEx on local and systemic IGF-I, as an explanatory factor in the physical function changes of older HIV+ and HIV- adults.**

Approach: Previously sedentary older adults (aged 50-75 years) will undergo a 24 week REx + CEx exercise training intervention.

Hypothesis 2a: HIV+ older adults will have lower *systemic* IGF-I at baseline and at week 20 compared to HIV- adults, with blunted response to exercise training.

Hypothesis 2b: HIV+ older adults will have lower baseline and lower week 20 *skeletal muscle* IGF-I mRNA and IGF-I protein, compared to HIV- adults

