  - Participants will be encouraged to avoid a large meal before exercise (snack is ok and encouraged). Blood pressure will be monitored before exercise, after the CVEx, and after the REx. As the expected response to exercise would be an increase in blood pressure, the PI will be contacted for any decreases in blood pressure after exercise.
5. **Week 12.**
  - Full physical function, anthropomorphics, questionnaires will be administered on Monday of week 12
  - The **Acute Inflammation visit 2** will occur on Thursday morning of week 12 (**beginning between 7:30-10am**). Arrangements for alternative dates can be made, but the participant must have at least 48 hrs from the prior exercise session). Participants will be encouraged to avoid a large meal before exercise (snack is ok and encouraged). Blood pressure will be monitored before exercise, after the CVEx, and after the REx. As the expected response to exercise would be an increase in blood pressure, the PI will be contacted for any decreases in blood pressure after exercise.
6. **Randomization/Week 13 visit.** At week 13, participants remaining on study will be randomized to either continue moderate intensity or advance to a higher-intensity exercise regimen with the randomization sequence generated by the study statistician ([name]).
  - V02, 1-RM will be measured on Monday of this week to develop a new prescription.
7. **Week 23.**
  - V02, 1-RM will be measured between Wed-Friday of this week.
8. **Week 24.**
  - **Acute inflammation visit 3.** During the week 24 of exercise, participants will be asked to exercise on Monday, Thursday, and Friday.
  - **Thursday (between 7:30-10 am)** will consist of a high intensity CV + REx exercise stimulus, and a blood draw prior to, and 0, 60, and 90 minutes following an exercise stimulus. Participants will be encouraged to avoid a large meal before exercise (snack is ok and encouraged). Blood pressure will be monitored before exercise, after the CVEx, and after the REx. As the expected response to exercise would be an increase in blood pressure, the PI will be contacted for any decreases in blood pressure after exercise.
  - Full physical function testing will occur on the final day of the exercise intervention
9. **Procedure visit #2.** Participants will return >48 hours after the last exercise session for a 2nd procedure visit for muscle biopsy (n=36), DXA scan, and blood draw.
  - DXA
  - Fasting for muscle biopsy (n=36)

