**2. Exercise testing and training:** All exercise intervention components will include 3 to 4 weekly, supervised sessions of combined CEx + REx at the University of Colorado-Denver (UCD) Exercise Research Laboratory (ERL). All participants will begin with a 2-week supervised, low-intensity exercise acclimation with an experienced research assistant. The initial goal will be to walk on a treadmill for 20-30 continuous minutes at low-intensity (30-40% of maximal aerobic power [VO2max]) and complete 3 sets of 8 repetitions at low-intensity (40-50% of the one-repetition maximum; 1-RM) 3 or 4 days/week. This will facilitate comfort with study equipment and minimize injury.

At 2 weeks, all participants will complete an additional 10 weeks of moderate- intensity exercise, with a goal of 50 minutes of cardiovascular + 3 sets of 8 resistance exercises by the end of the 12 week initial intervention. This will ensure that every participant meets at least the DHHS-PA recommendations in a supervised setting. At week 13, participants will be randomized to continue moderate intensity exercise, or progress to a high-intensity intervention for an additional 12 weeks.

*Maximal aerobic power (VO2 max).* The measurement of VO2max (or peak) will be used to formulate the prescription for CEx at the screening visit. Increases in VO2max in response to exercise training will also verify that the exercise was of sufficient intensity to induce cardiorespiratory adaptations. During an initial 5-min warm-up, walking speed will be adjusted to elicit a HR that is ~70% of maximal HR (from the screening GXT). Speed will then be held constant and the grade of the treadmill will be increased by 2% every 2 minutes until volitional exhaustion or until the test is stopped (see section 4.1.2b). The O2 and CO2 content of expired air will be measured continuously by open circuit spirometry and averaged every 30 sec using an automated online system (TrueMax 2400; ParvoMedics, Sandy, UT). Objective evidence that VO2max has been attained will include at least 2 of the following: a plateau in VO2 despite an increased energy demand, a respiratory exchange ratio in excess of 1.10, and a maximal HR within 10 beats of the age-predicted value. In the absence of these benchmarks, the maximum measured VO2 will be deemed VO2 peak.

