## **F. Data Analysis Plan:**

### **Statistical Considerations**

Sample Size Calculations: The primary outcome for sample size calculations is change from baseline in chair rise pace. We assume a change from baseline of 1.5 (SD=1.54) seconds or larger, based on differences observed by fall history [85]: Sample sizes of 36/group will yield an estimate of 29 patients per group at week 16 (~20% dropout). 29 subjects per group achieves over 80% power to detect a between group difference of 1.5 seconds with a significance level of 0.05 and the standard deviation conservatively estimated at 2.0 seconds[110] using a two-sided two-sample equal variance t-test.

Matching and Randomization: Enrollment in the uninfected arm will be constrained to lag behind HIV-enrollments. Upon the enrollment of every 5th HIV-infected patient, HIV-uninfected enrollment will be evaluated and recruiting goals updated to ensure a similar age (<60; >=60), gender, BMI, and smoking

distribution. Given the smaller proportion of women in the HIV-infected population, we plan to enroll fewer women. The randomization will be blocked by gender and exercise intensity to ensure balance according to the following scheme:

Exercise Intensity	Moderate (N=36)		High (N=36)	
HIV-Infected (N=36)	Men:	15	Men:	15
	Women:	3	Women:	3
Controls (N=36)	Men:	15	Men:	15
	Women:	3	Women:	3

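### The conclusion favouring higher-intensity exercise (section G, item 3) would rest on which HIV+ arm improves from week 0, not on a comparison of the randomised arms; the randomised counts and the week-16 label also need reconciling

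*Combined protocol and SAP*

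**What the plan says.** **Sample size (section F, Statistical Considerations).** The outcome is change from baseline in chair rise. "Sample sizes of 36/group will yield an estimate of 29 patients per group at week 16 (~20% dropout"), and "29 subjects per group achieves over 80% power to detect a between group difference of 1.5 seconds", with SD 2.0 s, two-sided 0.05 and a two-sample t-test. An SD of 1.54 s is also given for the assumed 1.5 s change.

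**Allocation (same section).** "The randomization will be blocked by gender and exercise intensity to ensure balance according to the following scheme". The table that follows has 36 moderate and 36 high, and 18 (15 men, 3 women) in each HIV-by-intensity cell.

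**Timing (sections C and D.2).** In the week-13 step of section C, "participants remaining on study will be randomized to either continue moderate intensity or advance to a higher-intensity exercise regimen". Section D.2 agrees: "At week 13, participants will be randomized to continue moderate intensity exercise, or progress to a high-intensity intervention for an additional 12 weeks". Before that, all participants have the same two-week lead-in and ten weeks at moderate intensity. In week 12, "Full physical function, anthropomorphics, questionnaires will be administered on Monday of week 12"; at the end, "Full physical function testing will occur on the final day of the exercise intervention".

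**Completion (Hypothesis 1c).** The two intensities "will result in similar completion rates, with 80% of participants completing the training program".

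**Analysis (section F, Analysis Plan).** A linear mixed model of change from week 0 has the baseline value and a group-and-time interaction. Group is HIV status or, alternatively, exercise intensity; the factor not used as group is a possible adjustment variable.

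**Interpretation (section G, item 3).** If HIV+ high intensity is the only group to improve in chair rise, this is taken as support for aiming future interventions at higher intensity.

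**The concern.** Item 3 turns a result in one cell into a recommendation about exercise intensity. A claim that high intensity is better for HIV+ adults needs the difference between the two HIV+ arms. Finding a significant change in one arm and not in the other does not supply it, because two arms with the same true gain will often fall on opposite sides of 0.05 when each has about 14 people. The change that item 3 looks at also starts at week 0, so a cell can improve because of the common first 12 weeks, whatever intensity does afterwards. The recommendation could therefore appear when intensity makes no difference.

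The second matter is bookkeeping. The allocation table adds up to everyone enrolled, yet only those still on study at week 13 are randomised. The 29 per group is dated to week 16, although training and final testing run to week 24. A reader could take 36 and 18 as the randomised numbers behind item 3, and cannot tell whether the 20% loss runs to week 16 or to week 24.

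**Working it through.** **Inputs.** From the documents: 72 enrolled, about 20% dropout, difference 1.5 s, SD 2.0 s (alternative 1.54 s), two-sided 0.05, randomisation at week 13, 80% completing. Assumed: the timing of loss, and that the two SDs apply to the quantities below. The documents give no SD for change after week 13. Power is from the noncentral t distribution at a single time point.

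**1. The plan's own figure.** 36 × 0.80 = 28.8, rounded to 29. SE = 2.0 × √(2/29) = 0.525 s; noncentrality 1.5/0.525 = 2.86; df = 56; power 80.1%. With 28.8 per group at week 24 (Hypothesis 1c), power is 79.9%. The plan's figure is reproduced.

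**2. Counts.** 4 × 18 = 72, which is everyone enrolled. If a fraction f is lost before week 13, 72 × (1 − f) are randomised:

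| Loss before week 13 | Randomised | Per arm | Per cell |
|---|---|---|---|
| 0% | 72 | 36 | 18 |
| 5% | 68 | 34 | 17 |
| 10% | 65 | 32 | 16 |
| 20% | 58 | 29 | 14 |

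If 80% of the 72 complete, about 28.8 per arm (14.4 per cell) are evaluable at week 24 in every row. The timing of loss changes the number randomised but not the pooled power.

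**3. How often item 3 could arise by chance.** Take 14 per cell, a true improvement of 1.5 s in each cell, and a one-sample t-test in each. The noncentrality is 1.5/(SD/√14).
- SD 2.0: noncentrality 2.81, chance of significance p = 0.737. High significant and moderate not: p(1 − p) = 0.737 × 0.263 = 0.194.
- SD 1.54: noncentrality 3.64, p = 0.920. p(1 − p) = 0.920 × 0.080 = 0.074.
- Strict reading, all three other cells non-significant: p(1 − p)³ = 0.013 (SD 2.0) or 0.0005 (SD 1.54).

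**4. The contrast that matches item 3.** High minus moderate within HIV+, 14 per cell, df = 26, critical t = 2.056:
- SD 2.0: SE = 2.0 × √(2/14) = 0.756 s; 95% CI half-width 1.55 s; power for 1.5 s is 48%.
- SD 1.54: SE = 0.582 s; half-width 1.20 s; power 70%.

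Two-weekly chair-rise data and adjustment for the week-12 value may improve on this, by an amount the documents do not let us quantify.

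**5. The interaction, for comparison.** SE = SD × √(4/14), df = 52. Power for a 1.5 s interaction is 28% (SD 2.0) or 43% (SD 1.54). It also estimates something else: if high beats moderate by 1.5 s in both HIV groups, the interaction is 1.5 − 1.5 = 0.

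**The case against.** The other side has good points, and several of them limit what can be claimed.

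- **The power arithmetic is right.** A reader might infer from the week-13 randomisation that the trial is underpowered. It is not, for a pooled comparison: step 2 shows the same evaluable number under Hypothesis 1c whenever loss occurs.
- **A lower power of about 75% at week 24 is tempting.** It comes from continuing the week-16 loss at the same rate: 36 × 0.8^1.5 = 25.8 per group. That implies about 28% loss by week 24, against the 80% completion that the protocol expects, and it ignores the repeated measures. It should not be written into the plan.
- **Change from week 0 might be thought to bias high versus moderate.** It does not. Gain before week 13 precedes randomisation and cancels in expectation between the arms. It misleads only when a single cell's improvement is interpreted.
- **An HIV-by-intensity interaction might seem the natural basis for item 3.** It asks whether HIV status modifies the intensity effect. It would be zero when Hypothesis 1b holds equally in both HIV groups, and so would deny support for higher intensity when that support is real.
- **Item 3 is conditional narrative, and nothing says it will be judged by separate p-values.** This is true, and the 19% and 7% depend on that reading. But the Analysis Plan names no between-arm contrast within HIV+ that could take its place, and the wording of item 3 points to cell-by-cell judgement.

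**Conclusion.** The concern holds, in two parts of unequal weight.

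The main part is item 3. It links an intensity recommendation to improvement in one cell, and no planned contrast supports that link. If both HIV+ arms truly improve by 1.5 s and each is tested separately at 14 per cell, the misleading two-arm pattern occurs in about 19% of trials (SD 2.0) or 7% (SD 1.54). Under the literal four-cell reading the risk is 1.3% or less, so the size of the problem depends on how item 3 would be applied. The figures also assume single-time-point tests and the plan's SDs.

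The second part is labelling. The allocation table can describe those randomised only if nobody is lost before week 13, and week 16 matches no stated endpoint. Neither affects the roughly 80% power of the pooled comparison when 80% complete. The HIV-status comparison from week 0 stands as planned.

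**What to change.** **(a) Item 3.** Base it on the high-minus-moderate difference within HIV+ participants randomised at week 13, in chair-rise change after randomisation, adjusted for the week-12 value already collected, with its 95% CI. Do not base it on which cell improves. Label it exploratory and state the expected precision from step 4, with the caveat about the SD after week 13. Report an HIV-by-intensity interaction only as a secondary check on whether the intensity effect differs by HIV status. Analyse the Hypothesis 1b comparison in randomised participants with the same week-12 adjustment. Participants lost before week 13 have no arm and stay in the HIV-status comparison from week 0.

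**(b) Counts.** Label 36 per arm and 18 per cell as enrolment targets. State that the number randomised depends on when loss occurs: 29 per arm and 14 per cell if all 20% are lost before week 13, up to 36 and 18 if none are.

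**(c) Time point.** Reconcile week 16 with week 24. Tie 29 per group and about 80% power to week 24 under Hypothesis 1c, and say that this power covers the pooled comparison only.

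**Cost.** No extra participants or visits. There is one more exploratory estimate with a wide interval (about ±1.6 s at SD 2.0, ±1.2 s at SD 1.54), so item 3 may have to be reported as inconclusive.

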## C. Study Design and Research Methods

Potentially eligible subjects will be screened during routine clinic visits or over the telephone. Potentially eligible and interested subjects will return for informed consent and a screening/baseline visit. No research procedures will occur prior to consent, including the MOCA.

After obtaining informed consent, participants will undergo a graded exercise test to screen for potential underlying cardiovascular disease. V02 peak will be measured at this time to develop the exercise prescription. All participants will begin with a low intensity lead-in for 1-2 weeks, then advance to a moderate intensity exercise during first 12 weeks. Randomization to continue on moderate versus advance to high intensity will occur at week 13.

**1. Consent & baseline visit.** After obtaining consent, the participant will be evaluated

-After obtaining consent, the participant will be evaluated by

- medical history, physical examination including vital signs
- Montreal Cognitive Assessment (MOCA)
- Resting BP, 12-lead resting ECG, and then a graded exercise test (GXT) administered by research personnel and a clinician experienced in exercise stress testing of older adults ([name]) to screen out volunteers with evidence of ischemic heart disease, serious arrhythmias, or abnormal HR/BP responses to exercise. Briefly, the test will begin at a comfortable walking speed and 0% elevation; speed will be maintained and the grade increased by 2% every 2 min, until the participant reaches 85% of age-predicted maximal heart rate or the test is otherwise terminated. The absolute and relative indicators for terminating an exercise test that are recommended by the American College of Sports Medicine (ACSM) will be employed.
- Baseline physical function assessments will be administered.

**2. Procedure visit #1 (within 14 days of visit #1).** All participants will arrive between 7:30-8am for:

- DXA scan
- Vital signs
- Anthropometrics (waist/hip circumference)
- Blood draw (fasting)
- 36 (up to 46, if needed to ensure 36 paired biopsy samples) volunteer participants (18 HIV+/18 HIV-) will have a muscle biopsy
  - If muscle biopsy at the end of the study cannot be done (patient refuses, change in medications, etc), then the number of biopsies will increase to a maximum of 46 in order to ensure each group has at least 18 paired (entry/completion) biopsy samples.
- Questionnaires

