**Analysis Plan:** Given repeated measurements over time, a linear mixed effects model will be used with change from week 0 as the primary outcome. The inclusion of additional time points will provide additional power. Groups defined by HIV-status (Exercise Intensity) will be evaluated. The baseline value and a group and time interaction term will be included as model predictors. The primary analysis will be intent to treat. Baseline (week 0) characteristics will be compared between groups prior to comparisons of endpoints, with log transformation for normality, as appropriate. The primary analysis will consider adjusting for age, smoking, exercise intensity (HIV-status) and body mass index (BMI); although if matching and/or balance by group is achieved, they may be precision variables, but they cannot be confounders. Finally, given the potential for non-ignorable dropout, we will accommodate dropout in the analysis of functional measures using a semi-parametric varying-coefficient model approach [150]. The primary analyses will assume that the slope beyond dropout is linear with sensitivity analyses utilizing a slope is attenuated by 50% and a zero slope beyond dropout, the latter being similar to a last value carried forward. Additionally a sensitivity analysis using only data from study completers will be conducted.

Change in IGF-I mRNA will be a primary outcome in the subset of participants undergoing muscle biopsy.

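### Intensity is randomised at week 13 but analysed as change from week 0, so chair-rise values collected before randomisation are not used to sharpen the trial's only randomised comparison (with time coded by visit)

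*Combined protocol and SAP*

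**What the plan says.** Section F (Data Analysis Plan, Analysis Plan) gives one model for two contrasts: "Given repeated measurements over time, a linear mixed effects model will be used with change from week 0 as the primary outcome". On groups: "Groups defined by HIV-status (Exercise Intensity) will be evaluated". On predictors: "The baseline value and a group and time interaction term will be included as model predictors". Baseline is defined there as week 0. The other covariates to be considered are age, smoking, BMI and whichever of the two factors is not being tested. Repeated visits are credited with a benefit: "The inclusion of additional time points will provide additional power". The coding of time is not stated, but the dropout method is framed in slopes: "The primary analyses will assume that the slope beyond dropout is linear with sensitivity analyses".

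Section C (Study Design and Research Methods) places the intensity allocation midway through the study: "At week 13, participants remaining on study will be randomized to either continue moderate intensity or advance to a higher-intensity exercise regimen". Section D.2 has everyone follow the same programme until then. Section C, item 3, has chair rise measured every two weeks, and item 5 puts full function testing on the Monday of week 12. No section makes a week 2-12 value a covariate for intensity or holds the arms equal before week 13.

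For resting IL-6, TNF-alpha and sTNFRI, section F compares groups on relative change from week 2 to week 24. Section D.5 also collects a pre-exercise sample at week 12.

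**The concern.** For HIV status, weeks 2-12 follow the exposure and belong among the outcomes. For intensity they are pre-randomisation measurements of the outcome variable, and usually the best predictors of it. If the model allows a free group difference at every visit, entering them as outcomes contributes nothing to the week-24 intensity contrast when data are complete. The claim of additional power then fails for those visits.

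Intensity is the only randomised comparison. Hypothesis 1b and the 24-week resting-marker hypothesis in Specific Aim 3 rest on it. The comparator arm also trains, so a true difference below the 1.5 s used for sizing is plausible, and there the lost precision counts.

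Two conditional problems follow from the same shared model. If time is a single linear slope from week 0, the arms may diverge before they have been randomised. And if intensity is a covariate in the HIV analysis, people who leave before week 13 have no randomised value, and no coding rule is given.

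**Working it through.** **1. The plan's own figure.** Section F: 29 per group, 1.5 s, SD 2.0 s, two-sided 0.05. SE = 2.0 × √(2/29) = 0.525 s; 1.5/0.525 = 2.86; noncentral t with 56 df gives 80.1%. The stated figure reproduces.

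**2. Assumptions.** No chair-rise correlation is given. I take 0.7 between weeks 0 and 24, the paired value in the Table 3 footnote (which concerns inflammatory markers). The SD of the week 0-24 change is 2.0 s, so the SD at one visit is 2.0/√(2 × 0.3) = 2.58 s. Visits are weeks 0, 2, …, 24; 29 per arm (N = 58); complete data. Three covariance patterns: constant correlation; AR(1) plus measurement error (error share 1 − √0.7 = 16%); AR(1).

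**3. Formula.** With p estimated covariates, variance of the contrast = residual variance × (2/29) × (N−3)/(N−3−p). Power comes from the noncentral t with N−2−p df.

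- Planned model (week 0 only): residual SD = 2.58 × √(1 − 0.49) = 1.844 s. SE = √(3.400 × 2/29 × 55/54) = 0.489 s.
- Week 0 plus mean of weeks 8, 10 and 12, constant correlation: the mean has relative variance (1 + 2 × 0.7)/3 = 0.8 and covariance 0.7 with weeks 0 and 24. The coefficients are 0.07/0.31 and 0.21/0.31, so the residual fraction is 1 − 0.7 × 0.28/0.31 = 0.368. Residual SD = 1.566 s; SE = √(2.452 × 2/29 × 55/53) = 0.419 s.

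| Week-24 contrast | Constant | AR(1) + error | AR(1) |
|---|---|---|---|
| Planned: SE (s) | 0.489 | 0.489 | 0.489 |
| Planned: power 1.0 s / 1.5 s | 52% / 85% | 52% / 85% | 52% / 85% |
| Week 0 + mean 8-12: SE (s) | 0.419 | 0.409 | 0.391 |
| Variance cut | 27% | 30% | 36% |
| Power 1.0 s / 1.5 s | 65% / 94% | 67% / 95% | 71% / 96% |
| Variance cut, mean 8-12 instead of week 0 | 24% | 31% | 37% |
| Variance cut, week 12 alone | 0% | 19% | 41% |
| Variance cut, all seven week 0-12 values | 25% | 24% | 34% |

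The gain equals 36-56% more participants (0.489²/0.419² = 1.36; 0.489²/0.391² = 1.56). Simulation with 20,000 trials per pattern gave cuts of 26.3%, 30.7% and 36.0%. With the week 0-24 correlation between 0.5 and 0.8 the cut is 18-39%. At week 16, the visit the sample size refers to, it is 27%, 39% and 63%. If the week 8-12 values carried no information, the extra covariate would cost 54/53 − 1 = 1.9% in variance.

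**4. Do early visits help as outcomes?** Generalised least squares, constant correlation 0.7, coefficients treated as known: with a free group difference at every visit the week-24 SE is 0.484 s, the same as using week 0 alone (1.844 × √(2/29)). Holding the arms equal through week 12 gives 0.396 s, 33% less variance.

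**5. If time is one linear slope from week 0.** The fitted week-24 difference is 0.67-0.99 of the truth when the effect ramps up after week 12, and 1.00-1.35 of it when the effect is a step. The ranges cover equal and generalised-least-squares weights, with and without a group main effect.

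**6. Resting markers.** Table 3 inputs: IL-6 log SD 0.629, 13 per group, 80% power. Assume correlation 0.7 between each pair of weeks 2, 12 and 24.

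- Change from week 2: SD = 0.629 × √0.6 = 0.487; detectable increase 75%.
- Adjusting for weeks 2 and 12: SD = 0.629 × √(1 − 2 × 0.49/1.7) = 0.409; detectable increase 64% with estimated coefficients.
- Correlation 0.5: 106% falls to 86%. Correlation 0.8: 58% falls to 50%.
- TNF-alpha at 0.7: 27.5% falls to 23.9%. sTNFRI: 24.8% falls to 21.6%.

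**7. Leavers before week 13.** 20% of 72 is about 14. Spread evenly to week 24, 14 × 13/24 is about 8; spread to week 16, 14 × 13/16 is about 11; at most 14.

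**The case against.** The strongest reply is that nothing fails. The estimate is unbiased on the main reading, the stated power reproduces, and the planned model already has 85% power for 1.5 s. The 1.0 s difference is illustrative; no section names it as a target. All of that stands, and it is why this is an efficiency point.

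The size is also conditional. Section F does not state the time coding and expects about 20% dropout, so data will not be complete. Under a linear slope and constant correlation the SE would be 0.321-0.374 s, smaller than the recommended model's 0.419 s. The trouble is then misestimation, as in step 5, and no longer lost precision; under AR(1) the slope model's SE is 0.489 s and the loss remains. This too stands. Neither reading favours the present wording.

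Section F also gives an SD of 1.54 s. If that applied to change, the planned model would have 74% power for 1.0 s and 97.5% for 1.5 s. The proportional variance cut does not depend on the SD: the recommended SEs scale by 1.54/2.0 to 0.323, 0.315 and 0.301 s, giving 86-90% for 1.0 s.

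The week 8-12 mean is one of several defensible covariates, and week 12 alone does better under AR(1). But week 12 alone gains nothing under constant correlation, whereas week 0 plus the mean gains under all three patterns.

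For IL-6, Table 3 prints 110% between groups. Its correlation footnote is attached to the within-group columns only, so my 75% is a separate calculation for change from week 2 and does not correct the table. Section F names no model for this comparison; the lack of adjustment is read from its description.

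**Conclusion.** The point holds. One change-from-week-0 model serves two contrasts that need different baselines, and prognostic values already collected before the week-13 randomisation are not used for the intensity comparison. With categorical time and complete data the cost is precision only. Adding the week 8-12 mean would cut the week-24 variance by 27-36% (18-39% over correlations of 0.5-0.8) and raise power for a 1.0 s difference from 52% to 65-71%. The fact of the omission is certain. Its size rests on an assumed correlation, three assumed covariance patterns and an SD of change of 2.0 s; every pattern examined showed a gain. The distortion under a linear slope and the handling of early leavers in the HIV analysis are conditional on choices the plan has not stated. The within-visit acute comparisons are not affected. It should be fixed as a free improvement.

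**What to change.** Write separate models for the two contrasts.

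1. **Intensity.** Analyse those randomised at week 13. Use post-randomisation visits as outcomes with categorical time, or keep all visits and fix the group difference at zero before week 13. Adjust for the week-0 value and the mean of the week 8, 10 and 12 chair-rise values, and include HIV status and gender. State what happens when one of those three values is missing (for example, average those available), since section C, item 3, expects absences.
2. **Resting IL-6, TNF-alpha and sTNFRI at week 24, between arms.** Adjust for the week-2 and week-12 pre-exercise log values. Leave the acute comparisons as they are.
3. **HIV status.** Keep week 0 as baseline. If intensity is adjusted for, enter it as time-varying, zero before week 13, so that early leavers stay in the intent-to-treat analysis.

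State the time coding for each model, and align the dropout method with the split. The cost is analysis-plan wording and some care with the dropout model; no visit, sample or participant is added.
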